[figure not shown]
[figure not shown]

[figure not shown]
[figure not shown]
[figure not shown]

## CLINICAL TRIAL PROTOCOL SYNOPSIS

Company name	Boehringer Ingelheim
Protocol date	22 June 2020
Revision date	Not applicable
BI trial number	1405-0015
Title of trial	Relative bioavailability of rosuvastatin (Part 1) and dabigatran (Part 2) given alone and together with BI 1323495 in healthy male subjects (open, single-dose, randomised, two-period crossover design in each trial part)
Principal Investigator:	[REDACTED]
Trial site	
Clinical phase	I
Trial rationale	BI 1323495 has been characterised to be an inhibitor of P-gp, OATP1B1 and BCRP in-vitro . This trial will be performed to test the inhibitory effect of BI 1323495 on these drug transporters in-vivo . Dabigatran will be used as model substrate for P-gp, rosuvastatin as model substrate for BCRP and OATP1B1.
Trial objectives	To investigate the relative bioavailability of 10 mg rosuvastatin (Part 1) and 150 mg dabigatran (Part 2) given alone and together with [REDACTED] BI 1323495
Trial design	Randomised, open-label, two period crossover design in each trial part
Trial endpoints:	Part 1 Primary endpoints: AUC 0-∞ and C max of rosuvastatin Secondary endpoint: AUC 0-tz of rosuvastatin Part 2 Primary endpoints: AUC 0-∞ and C max of dabigatran Secondary endpoint: AUC 0-tz of dabigatran
Number of subjects total entered each treatment	28: 14 in Part 1 and 14 in Part 2 14
Diagnosis	Not applicable
Main criteria for inclusion	Healthy male subjects, age of 18 to 55 years (inclusive), body mass index (BMI) of 18.5 to 29.9 kg/m  (inclusive) genotyped as UGT2B17 extensive metabolizers
Test product 1 dose mode of admin.	Rosuvastatin (Crestor ® 10 mg Filmtabletten) 10 mg (1 tablet) Oral with 240 mL of water after a standardised breakfast

Test product 2 dose mode of admin.	Dabigatran etexilate (Pradaxa® 75 mg Hartkapseln) 75 mg (1 capsule) Oral with 240 mL of water after a standardised breakfast
Test product 3 dose mode of admin.	BI 1323495 [REDACTED] [REDACTED] Oral with 240 mL of water after a standardised breakfast
Duration of treatment	Part 1 Treatment R1: 10 mg rosuvastatin as single dose on study day 1 of period 1 or 2 Treatment T1: 10 mg rosuvastatin + [REDACTED] g BI 1323495 as single dose on study day 1 of period 1 or 2  Drug administrations in period 1 and 2 are separated by a wash-out period of at least 7 days.  Part 2 Treatment R2: 75 mg dabigatran as single dose on study day 1 of period 1 or 2 Treatment T2: 75 mg dabigatran + [REDACTED] BI 1323495 as single dose on study day 1 of period 1 or 2  Drug administrations in period 1 and 2 are separated by a wash-out period of at least 7 days.
Statistical methods	Relative bioavailability will be estimated by the ratios of the geometric means (test/reference) for the primary and secondary endpoints. Additionally, their two-sided 90% confidence intervals (CIs) will be provided. This method corresponds to the two one-sided t-test procedure, each at a 5% significance level. Since the main focus is on estimation and not testing, a formal hypothesis test and associated acceptance range is not specified. The statistical model will be an analysis of variance (ANOVA) on the logarithmic scale including effects for sequence, subjects nested within sequences, period and treatment. CIs will be calculated based on the residual error from the ANOVA.  Descriptive statistics will be calculated for all endpoints.

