#### *Dabigatran*

[figure not shown]
In trial 1160.60 a single dose of 600 mg dabigatran etexilate was well tolerated by healthy subjects [[U06-1614-01](#)]. Taking into account the dose-proportional kinetics of dabigatran, the well tolerated single dose of 600 mg provides a safety margin of 4 to the therapeutic dose of 150 mg daily and of 8 to the dose being used in Part 2 of this trial (75 mg).

Dabigatran etexilate is a sensitive substrate of intestinal P-gp. The effect of several P-gp inhibitors has been tested in healthy subjects. The strongest effects have been seen with a single dose of verapamil given 1 hour before dabigatran intake (2.8 fold increase of dabigatran  $C_{max}$ ) and with multiple doses of ketoconazole (2.5 fold increase of dabigatran  $C_{max}$  und AUC) [R19-3343]. The observed increase in dabigatran exposure has been well tolerated by healthy subjects, which is in line with the described safety margin of 4 at a dose of 150 mg, that has not been exceeded by any P-gp inhibitor.

No undue risk to healthy subjects is expected from the combined administration of 75 mg dabigatran etexilate and BI 1323495 in this trial.

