## 2. TRIAL OBJECTIVES AND ENDPOINTS

### 2.1 MAIN OBJECTIVES, PRIMARY AND SECONDARY ENDPOINTS

#### 2.1.1 Main objectives

The main objectives of this trial are to investigate the relative bioavailabilities of 10 mg rosuvastatin (Reference 1, Part 1) and 75 mg dabigatran (Reference 2, Part 2) given alone and together with 300 mg BI 1358894 (Test 1, Test 2) following oral administration.

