### 3. DESCRIPTION OF DESIGN AND TRIAL POPULATION

#### 3.1 OVERALL TRIAL DESIGN AND PLAN

The study comprises two trial parts. Each part follows a randomised, open-label, two-period crossover design in healthy male subjects in order to compare the following test and reference treatments:

##### Treatments in Part 1

- Reference (R1): 10 mg rosuvastatin as single dose on study day 1 of period 1 or 2
- Test (T1): 10 mg rosuvastatin together with [REDACTED] BI 1323495 as single dose on study day 1 of period 1 or 2

##### Treatments in Part 2

- Reference (R2): 75 mg dabigatran etexilate as single dose on study day 1 of period 1 or 2
- Test (T2): 75 mg dabigatran etexilate together with [REDACTED] BI 1323495 as single dose on study day 1 of period 1 or 2

All treatments will be given after a standardised meal. Drug administrations in period 1 and 2 will be separated by at least 7 days. For details refer to Section [4.1](#).

An overview of all relevant trial activities is provided in the [Flow Chart for Part 1](#) and [Part 2](#). For visit schedule and details of trial procedures at selected visits, refer to Sections [6.1](#) and [6.2](#), respectively.

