6. GENERAL ANALYSIS DEFINITIONS

6.1 TREATMENTS

For basic study information on investigational products, assignment of treatment sequences and selection of doses, please see CTP, Sections 3 and 4.

The study consists of 2 trial parts, Part 1 with rosuvastatin and Part 2 with dabigatran. It is planned that within each part of the study, 14 healthy male subjects will enter. Each part follows an open-label, randomized, two-period, two-way crossover design in order to compare the test (B, D) and reference (A, C) treatments as defined in Table 6.1: 1 below.

Table 6.1: 1 Treatments and labels used in the analysis

Treatment	Short label
Part 1	
A Rosuvastatin, 10 mg tablet, qd	Rosu
B BI 1323495, 6*50 mg tab + Rosuvastatin, 10 mg tab, qd	BI+Rosu
Part 2	
C Dabigatran etexilate, 75 mg capsule, qd	Dabi
D BI 1323495, 6*50 mg tab + Dabigatran etex, 75 mg caps, qd	BI+Dabi

Section 1.2.4 of CTP:

The Residual Effect Period (REP) of BI 1323495, rosuvastatin, and dabigatran, i.e. the period after the last dose with measurable drug levels and/or pharmacodynamic effects still likely to be present, will be defined as 7 days for each of the 3 products.

The following study phases in Part 1 and Part 2 will be defined for the analysis of adverse events (AEs):

- **Screening** (ranging from 0:00 h on day of informed consent until first administration of study medication in treatment period 1)
- **On treatment** (ranging from the time of administration of test or reference treatment until administration time of next study drug dose or until 0:00 h on day 7 after time of administration, whatever occurs first)

→ labelled **Rosu, BI+Rosu, Dabi, BI+Dabi**

- **Follow-up (F/U)** (ranging from 0:00 h on day 7 after the time of administration of test or reference treatment until administration time of next study drug dose or until 0:00 h on day after trial termination date, whatever occurs first)

→ labelled **F/U Rosu, F/U BI+Rosu, F/U Dabi, F/U BI+Dabi**

Section 7.3.4 of the CTP: *Note that AEs occurring after the last per protocol contact but entered before final database lock will be reported to Pharmacovigilance only and will not be captured in the trial database.*

The following AE displays will be provided in the report:

Section 15.3 and Appendix 16.1.13.1.8 (for ClinicalTrials.gov and EudraCT only) of the CTR displays:

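### Do the 150 mg dabigatran dose and the different compound code in two statements of the objective leave the trial's comparison undefined?

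*Protocol*

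**What the plan says.** The protocol states its main objective three times.

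- **Synopsis, objectives row:** it reads "To investigate the relative bioavailability of 10 mg rosuvastatin (Part 1) and 150 mg dabigatran (Part 2) given alone and together with". The compound named next is BI 1323495, whose dose is redacted.
- **Section 2.1.1:** 10 mg rosuvastatin and 75 mg dabigatran, "given alone and together with 300 mg BI 1358894 (Test 1, Test 2) following oral administration".
- **Section 7.1:** 10 mg rosuvastatin and 75 mg dabigatran, alone and with BI 1323495.

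The treatments are described separately. The synopsis lists test product 2 as "75 mg (1 capsule) Oral with 240 mL of water after a standardised breakfast" and the reference as "Treatment R2: 75 mg dabigatran as single dose on study day 1 of period 1 or 2". Section 3.1 has "Reference (R2): 75 mg dabigatran etexilate as single dose on study day 1 of period 1 or 2". Section 4.1.1 gives a unit strength of 75 mg and one capsule per administration, and Table 4.1.4: 1 gives a total dose of 75 mg in both Part 2 treatments. SAP Table 6.1: 1 defines the Part 2 test treatment as "BI 1323495, 6*50 mg tab + Dabigatran etex, 75 mg caps, qd". Section 1.4 gives a safety margin "of 8 to the dose being used in Part 2 of this trial (75 mg").

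**The concern.** The trial's main output is a set of test/reference ratios with 90% confidence intervals and no acceptance range, so the objective should say exactly what is compared. Read alone, the synopsis objective has a dabigatran dose twice that in the treatment sections, and Section 2.1.1 names a co-administered drug that is not the trial's investigational product. SAP Section 3 also sends readers to the protocol for the study objectives, where they meet both entries.

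Three things could be at stake: what is given, what is estimated, and whether the benefit-risk argument holds. On the last, the protocol's margin against the tolerated 600 mg dose would be half as large at 150 mg as at 75 mg.

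**Working it through.** **1. The entries side by side**

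| Place | Dabigatran, Part 2 | Co-administered drug |
|---|---|---|
| Synopsis, objective | 150 mg | BI 1323495 |
| Synopsis, test products and R2/T2 | 75 mg | BI 1323495 |
| Section 1.4 | 75 mg | BI 1323495 |
| Section 2.1.1 | 75 mg | BI 1358894, 300 mg |
| Section 3.1 | 75 mg | BI 1323495 |
| Sections 4.1.1 and 4.1.4 | 75 mg | BI 1323495 |
| Section 7.1 | 75 mg | BI 1323495 |
| SAP Table 6.1: 1 | 75 mg | BI 1323495, 6 × 50 mg |

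Each of the two conflicting statements differs from the rest in one entry only. In Section 2.1.1 the amount agrees with the SAP (6 × 50 mg = 300 mg), so only the code differs. The figure of 150 mg does occur elsewhere in the protocol: Section 1.2.3 has it as a daily dose made up of 75 mg capsules, and Section 1.4 as the daily therapeutic dose. Neither place gives it as the Part 2 dose.

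**2. Does the analysis use either odd entry?** The model in protocol Section 7.3.1 and SAP Section 7.4.1 works on treatment labels. SAP Table 6.1: 1 defines those labels itself. SAP Section 3 rests the analysis on protocol Section 7, which holds the consistent statement, and SAP Section 6.1 refers to protocol Sections 3 and 4 for products and doses. SAP Section 5 quotes protocol Sections 2.1.2 and 2.1.3, not 2.1.1. Neither odd entry appears in the SAP.

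**3. Does the precision depend on the dose?** Table 7.7: 1 can be reproduced with n = 12 and

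precision = exp{ t(0.95, n−2) × √ln(1+CV²) × √(2/n) × √[χ²(0.95, n−2)/(n−2)] }.

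| gCV | Protocol | Reproduced | 90% CI at ratio 100% |
|---|---|---|---|
| 10% | 1.105 | 1.1050 | 90.50 to 110.50 |
| 20% | 1.219 | 1.2193 | 82.01 to 121.93 |
| 30% | 1.342 | 1.3416 | 74.54 to 134.16 |

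The only inputs are gCV and n. Section 7.7 gives a gCV of about 20% for dabigatran without tying it to a dose.

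**4. The safety margins.** 600/150 = 4 and 600/75 = 8. Both match Section 1.4, which names the dose that belongs to each margin, so that section can be read in only one way. The strongest P-gp effect it cites, 2.8-fold on Cmax, is below both. That figure is the protocol's own comparator and sets no bound on the effect of BI 1323495.

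**The case for a change.** The strongest case for a change is that an ethics committee and a competent authority approve the protocol, and many readers go first to the synopsis and the objectives. A document whose objective conflicts with its treatment table on the dose, and whose formal objectives section names another compound, is not in good order. Correcting it takes two text edits, and the amendment already made left both entries alone.

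The facts in this case stand. Both conflicts are in the current text, and neither comes from redaction or from reading the PDF. The claimed consequences do not stand. It is not true that no statement of the objective matches the treatments, because Section 7.1 does. The errors do not carry over into the SAP. The benefit-risk section does not depend on the synopsis wording. Nor is the edit free if made alone: under Section 8.1, changes introduced by an amendment need the same approvals as the protocol.

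**Conclusion.** The concern is right about the text, but no change to the plan follows. Two of the three statements of the objective each contain one clerical conflict: a factor of 2 in the printed dabigatran dose, and one compound code. The effect on the dosing instructions, the treatment contrast, the model, the precision table and the stated safety margins is nil.

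This rests on two points visible in the documents: the sections that direct dosing and analysis agree with one another, and none of them draws on the synopsis objective or Section 2.1.1 for a dose or a compound. The conflicting passages must still be reconciled, and the sponsor has to confirm the entries. This review takes no position on which dose is right. Reconciling them is document housekeeping.

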## FLOW CHART

### FLOW CHART PART 1 (ROSUVASTATIN)

Period	Visit	Day	Planned time (relative to drug administration) [h:min]	Approximate clock time of actual day [h:min]	Event and comment	Safety laboratory 	PK blood, Rosuvastatin	PK blood, BI 1323495	12-lead ECG	Vital signs (BP, PR)	Questioning for AEs and concomitant therapy 			
SCR	1	-21 to -1			Screening (SCR) 	X A			X	X				
1/2 (two identical periods separated by a wash-out of at least 7 days)	2/3	1	-2:00	06:00	Admission to trial site 	X B,2,3	X 	X 	X 	X 	X 			
			-0:30	07:30	Standardised breakfast									
			0:00	08:00	Drug administration									
			0:30	08:30					X 					
			1:00	09:00				X	X 					
			2:00	10:00	240 mL fluid intake			X	X 					
			3:00	11:00				X	X 					
			3:30	11:30				X						
			4:00	12:00	240 mL fluid intake			X	X 					
			4:30	12:30				X						
			5:00	13:00	Lunch 			X	X 				X	
			5:30	13:30				X						
			6:00	14:00				X	X 					
			7:00	15:00				X						
			8:00	16:00	Snack (voluntary) 			X	X 					
			10:00	18:00				X						
			11:00	19:00	Dinner									
			12:00	20:00				X	X 				X	
			2	24:00	08:00	Breakfast (voluntary) 			X B	X	X 	X	X	X
				28:30	12:30	Lunch (voluntary) 								X
32:00	16:00	Snack (voluntary)												
34:00	18:00	Discharge from trial site					X				X			
3	47:00	07:00	Ambulatory visit			X				X				
4	71:00	07:00	Ambulatory visit			X				X				
5	95:00	07:00	Ambulatory visit			X				X				
FU	4	8 to 15			End of trial (EoTrial) examination 	X C			X	X	X			

- Subject must be informed and written informed consent obtained prior to starting any screening procedures. Screening procedures include physical examination, check of vital signs, ECG, safety laboratory (including drug screening), [REDACTED] demographics (including determination of body height and weight, smoking status and alcohol history), relevant medical history, concomitant therapy and review of inclusion/exclusion criteria. [REDACTED]
- The time is approximate; the procedure is to be performed and completed within the 3 h prior to drug administration.
- Includes urine drug screening and alcohol breath test

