### **3.3.2 Inclusion criteria**

Subjects will only be included in the trial if they meet the following criteria:

1. Healthy male subjects according to the assessment of the investigator, as based on a complete medical history including a physical examination, vital signs (BP, PR), 12-lead ECG, and clinical laboratory tests
2. Age of 18 to 55 years (inclusive)
3. BMI of 18.5 to 29.9 kg/m^2 (inclusive)
4. Signed and dated written informed consent prior to admission to the study, in accordance with GCP and local legislation

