#### **7.7 DETERMINATION OF SAMPLE SIZE**

It is planned to enter 14 subjects in each trial part (accounting for up to 2 dropouts or non PK evaluable subjects). The planned sample size is not based on a power calculation but is considered sufficient to achieve the aims of this exploratory trial. With this sample size, the following precision in estimating the ratio of geometric means (test/reference) can be expected with 95% probability. Precision is defined as the ratio of upper CI limit to the relative BA estimate. Note that the precision is independent of the actual ratio of geometric means.

The observed intra-individual coefficient of variation (gCV) for rosuvastatin ranged from from 9.0 to 19.7% for AUC and from 14.1 to 28.4% for  $C_{max}$ , whereas the observed intra-individual coefficient of variation (gCV) for dabigatran were ~20% for  $C_{max}$  as well as for AUC in previous trials [[c08983809-01](#), [c13060859-01](#), [U09-3249-02](#)].

For various assumptions around the gCV, Table 7.7: 1 provides an overview of the achievable precision for estimating the ratio of geometric means (test/reference). For illustrative purposes, the expected 90% confidence intervals with 95% tolerance probability are displayed for different values of the ratios T/R of geometric means.

Table 7.7: 1 Precision that can be expected with 95% probability and illustrative two-sided 90% confidence intervals around the ratios of geometric means (T/R) for different gCVs in a 2x2 crossover trial ( $N=12$ )

gCV [%]	Precision upper CI limit / relative BA estimate	Ratio [%]*	Lower CI limit [%]	Upper CI limit [%]
10.0	1.105	100	90.50	110.50
10.0	1.105	150	135.74	165.75
10.0	1.105	200	180.99	221.00
20.0	1.219	100	82.01	121.93
20.0	1.219	150	123.02	182.89
20.0	1.219	200	164.03	243.86
30.0	1.342	100	74.54	134.16
30.0	1.342	150	111.80	201.25
30.0	1.342	200	149.07	268.33

\*Ratio of geometric means (test/reference) for a PK endpoint is defined by  $\exp(\mu_T)/\exp(\mu_R)$ .

The expected 90% confidence interval limits in the table were derived by

$$CI\ limit_{upper,lower} = \exp(\ln(\theta) \pm \omega),$$

with  $\theta$  being the ratio (T/R) on original scale and  $\omega$  the distance from the estimate  $\theta$  to either confidence interval limit on the log-scale, which was obtained from the achievable precision on the original scale.

The calculation was performed as described by Julious [[R11-5230](#)] using R Version 3.5.1.

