### **8.3.1 Source documents**

In accordance with regulatory requirements, the investigator should prepare and maintain adequate and accurate source documents and trial records for each trial subject that include all observations and other data pertinent to the investigation. Source data as well as reported data should follow the 'ALCOA principles' and be atttributable, legible, contemporaneous, original, and accurate. Changes to the data should be traceable (audit trail).

Data reported on the CRF must be consistent with the source data or the discrepancies must be explained.

Before providing any copy of subjects' source documents to the sponsor, the investigator must ensure that all subject identifiers (e.g., subject's name, initials, address, phone number, and social security number) have properly been removed or redacted to ensure subject confidentiality.

If the subject is not compliant with the protocol, any corrective action (e.g. re-training) must be documented in the subject file.

For the CRF, data must be derived from source documents, for example:

- Subject identification: sex, year of birth (in accordance with local laws and regulations)
- Subject participation in the trial (substance, trial number, subject number, date subject was informed)
- Dates of subject's visits, including dispensing of trial medication
- Medical history (including trial indication and concomitant diseases, if applicable)
- Medication history
- AEs and outcome events (onset date [mandatory], and end date [if available])
- SAEs (onset date [mandatory], and end date [if available])
- Concomitant therapy (start date, changes)
- Originals or copies of laboratory results and other imaging or testing results, with proper documented medical evaluation (in validated electronic format, if available)
- ECG results (original or copies of printouts)
- Completion of subject's participation in the trial (end date; in case of premature discontinuation, document the reason for it, if known)
- Prior to allocation of a subject to a treatment into a clinical trial, there must be documented evidence in the source data (e.g. medical records) that the trial participant meets all inclusion criteria and does not meet any exclusion criteria. The absence of records (either medical records, verbal documented feedback of the subject or testing conducted specific for a protocol) to support inclusion/exclusion criteria does not make the subject eligible for the clinical trial.

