6.2 IMPORTANT PROTOCOL DEVIATIONS

Data discrepancies and deviations from the CTP will be identified for all treated subjects.

Section 7.3 of the CTP: *Important protocol deviation (IPD) categories will be suggested in the IQRM plan, IPDs will be identified no later than in the Report Planning Meeting, and the IPD categories will be updated as needed.*

Consistency check listings (for identification of deviations of time windows) and a list of protocol deviations (e.g. deviations in drug administration, in blood sampling times, etc.) will be provided to be discussed at the Report Planning Meeting (RPM). At this meeting, all manual deviations identified at the sites by the CRAs and deviations too complex to program will be reviewed by the trial team to decide which are considered important. For definition of important protocol deviations (iPD), and for the process of identification of these, refer to the Boehringer Ingelheim (BI) SOP "Identify and Manage Important Protocol Deviations (iPD)" (2).

If any iPDs are identified, they are to be summarised into categories and will be captured in the decision log. Categories which are considered to be iPDs in this trial are defined in the integrated quality and risk management plan (IQRMP). An overview of the defined iPDs and if they could potentially lead to exclusion from defined analysis sets (see 6.3) is given in Table 6.2: 1. The decision on exclusion of subjects from analysis sets will be made at the latest at the Report Planning Meeting, after discussion of exceptional cases and implications for analyses. If the data show other iPDs, the definition in the IQRMP will be supplemented accordingly by the time of the Report Planning Meeting. The iPDs will be summarised and listed.

Table 6.2: 1 Important protocol deviations

Category/ Code	Description	Exclusion from
A	Inclusion/Exclusion Criteria	
A1	Inclusion Criteria Not Met	PKS
A2	Exclusion Criteria Violated	PKS
B	Informed consent	
B1	Informed consent not available/not done	TS / PKS
B2	Informed consent too late	none
C	Trial medication and randomization	
C1	Incorrect trial medication taken	PKS
C2	Randomisation not followed	PKS
C3	Non-compliance	PKS
C5	Incorrect intake of trial medication	PKS
C6	Improper washout between treatments	PKS
D	Concomitant medication	
D1	Prohibited medication use	PKS
E	Missing data	
E1	Certain deviations from procedures used to measure primary or secondary data	PKS

F		Incorrect timing	

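### Does the synopsis restrict entry to a UGT2B17 genotype that the inclusion criteria in Section 3.3.2 do not require?

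*Protocol*

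**What the plan says.** The synopsis row on main inclusion criteria names healthy men, an age range, a BMI range and subjects "genotyped as UGT2B17 extensive metabolizers".

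Protocol Section 3.3.2 opens with "Subjects will only be included in the trial if they meet the following criteria" and then shows four items: health, age, BMI and consent. The age and BMI limits match the synopsis. The last readable item is "Signed and dated written informed consent prior to admission to the study, in accordance with GCP and local legislation". UGT2B17 appears nowhere else in the readable protocol or SAP.

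Two other places depend on the entry criteria. Section 8.3.1 requires documented evidence before allocation "that the trial participant meets all inclusion criteria and does not meet any exclusion criteria". SAP Table 6.2: 1 lists deviation A1, "Inclusion Criteria Not Met", with the PKS in its exclusion column. The SAP text above that table treats such exclusion as a possibility and adds: "The decision on exclusion of subjects from analysis sets will be made at the latest at the Report Planning Meeting".

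**The concern.** Read as they stand, the two pages give different entry rules. A subject who is not an extensive metabolizer would breach the synopsis and comply with Section 3.3.2. Under the first reading he is a candidate for deviation A1 and may leave the PKS; under the second there is no deviation. With 14 subjects entered per part and 12 assumed evaluable, a few such subjects would matter to the primary analysis and to the population that the test/reference ratio describes.

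Several things make an omission look plausible. The readable items run from 1 to 4 without a gap or a black bar. None of the 27 exclusion criteria mentions genotype. Neither laboratory table lists a genotype test. And because the phrase is readable in the synopsis, there seems little reason to hide it elsewhere.

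**Working it through.** The concern needs the criterion to be absent from the plan, not merely from this public copy. Each supporting argument can be checked against the documents.

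**1. Does unbroken numbering show that nothing was removed?** No. Text has gone without a redaction mark in many places:
- Section 1.1 has a heading and no text.
- The numbering jumps from 2.1.3 to 2.2.2.4 and from 7.3.2 to 7.3.4.
- Sections 5.4 and 5.6 are absent, although Section 6.2.2 refers the reader to 5.4.
- The risk mitigation list in Section 1.4 contains an empty bullet.

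Consent is the last readable item in Section 3.3.2, so a removed item 5 would leave the sequence 1 to 4 intact.

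**2. Would a phrase readable in the synopsis be hidden elsewhere?** It could be, because redaction here is inconsistent. The BI 1323495 dose is blacked out in the synopsis, in Section 3.1, in Table 4.1.4: 1 and in Section 7.1. Yet SAP Table 6.1: 1 prints 6*50 mg, and protocol Section 2.1.1 prints 300 mg (there against a different compound number).

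**3. Are there removals where genotype text would sit?** Yes. The Part 1 screening footnote reads "safety laboratory (including drug screening), [REDACTED] demographics", so a screening item is blacked out. A second redaction follows directly after the review of inclusion and exclusion criteria. The Part 2 footnote has the same two redactions. The abbreviation list also breaks between TSAP and ULN, where UGT would sort; that is suggestive only.

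**4. Does absence from the laboratory tables show that a test is not done?** No. Faecal occult blood testing is described in Section 5.2.3 and the SARS-CoV-2 test is required by exclusion criterion 27; neither is in Table 5.2.3: 1 or 5.2.3: 2.

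**5. Is there a number at stake?** The plan's only sample-size figure is the precision in Table 7.7: 1:

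precision = exp( t(0.95, N−2) × √ln(1+gCV²) × √(2/N) × √(χ²(0.95, N−2)/(N−2)) )

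With N=12 this gives 1.1050, 1.2193 and 1.3416 for gCVs of 10, 20 and 30%, which matches the table's 1.105, 1.219 and 1.342. Genotype is not an input. It could act only by lowering N: at a gCV of 20%, precision would be 1.2577 with N=10 and 1.3215 with N=8.

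How many subjects might be affected cannot be taken from the documents. For an assumed share p of non-extensive metabolizers among 14 subjects:

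| Assumed p | At least 1: 1−(1−p)^14 | 3 or more (beyond the allowance of 2) |
|---|---|---|
| 5% | 0.512 | 0.030 |
| 10% | 0.771 | 0.158 |
| 20% | 0.956 | 0.552 |
| 30% | 0.993 | 0.839 |

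These values describe a sample enrolled without regard to genotype. To become a loss of precision, every link of a chain must hold: the criterion is truly absent from Section 3.3.2, no genotype is checked at screening, the affected subjects are later removed under A1, and they are not replaced. Section 3.3.5 allows replacement of subjects who are not PK evaluable.

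**The case for a change.** The strongest counter-argument is that the synopsis and the body are demonstrably not fully aligned elsewhere. The synopsis objective gives 150 mg dabigatran, whereas the synopsis treatment rows and Sections 2.1.1 and 3.1 give 75 mg; those passages need reconciling in their own right. An omission in Section 3.3.2 could have the same origin. A blacked-out genotyping procedure in the flow chart would also not by itself supply an eligibility criterion.

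Both remarks are fair, and the readable pages do differ. But they show only that an omission is possible. They do not rule out an unmarked removal, for which this copy offers many precedents.

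The stated consequences are also weaker than they look. The readable documents never say what UGT2B17 does for BI 1323495, so the idea that the restriction controls exposure to that compound has no support in them. Each subject is his own control (Section 3.2), so a mixed-genotype sample would not confound the test/reference ratio; it would change the population described. Nor do the documents give two answers on who is analysed. Protocol Section 7.3 excludes data only for deviations relevant to the PK evaluation, and the SAP assigns the decision to a named meeting.

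**Conclusion.** The concern does not hold as a finding against the plan. The difference between the synopsis and the readable Section 3.3.2 is real in this copy, but the copy cannot show that the criterion is missing from the protocol itself, and several of its removals fit genotype text. Material lost to redaction is not a gap in the plan.

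No effect size is established. The precision figures in Table 7.7: 1 reproduce and are independent of genotype, and the 3% to 84% range for exceeding the allowance of 2 rests wholly on assumed shares of 5% to 30% and on the full chain set out above.

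This conclusion rests on redaction being a live explanation, not a proven one. If the unredacted Section 3.3.2 had no genotype item, the synopsis and that section would disagree and the point would reopen as a consistency correction. That calls for a look at the page by the sponsor; it is not a demonstrated defect.
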